5.2 Exploratory objective(s)

If there is a synergistic effect of TRT and chemoimmunotherapy, the frequency of brain metastases may decrease in the experimental arm, or the time until brain metastases occur may be prolonged. Thus, we will compare the frequency and timing of brain metastases. To explore potential benefits or disadvantages of PCI, we will measure cognitive function before and after chemoimmunotherapy and PCI.

[figure not shown]
It is evident that not all ES SCLC patients benefit from durvalumab. Costs of new therapies has become an increasingly important issue. Identifying those who benefit the most from each therapy, will enable us to better individualize therapy for each patient. There are several benefits for both patients and society. Patients will avoid spending time for futile therapy, avoid unnecessary toxicity, and may be offered other, more effective treatments. More targeted therapy will reduce costs, but also better use of our health services' resources. Thus, the biomarker analyses may have significant implications for future clinical practice and research.

6. Study design

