14.1 Endpoints

Primary endpoint

• 1-year overall survival

Secondary endpoints

- 2-year, 3-year, 4-year and 5-year overall survival.
- Overall response rates
- Response rates in non-irradiated lesions
- Progression free survival
- Progression free survival in non-irradiated lesions
- Local control rates in the thorax
- Frequency and severity of adverse events
- Health-related quality of life

Exploratory endpoints

- Duration of severe adverse events
- Frequency and timing of brain metastases
- Assess cognitive function in the whole study cohort and compare cognitive function between patients who receive PCI and those who do not.
- Associations between outcomes of study treatment and biomarkers in tissue, blood and stool (e.g. ctDNA in blood, miRNA and gut microbiome).

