14.3.2 Efficacy analyses

For the primary endpoint, the Cox proportional hazards method will be used to compare survival between the treatment groups. Considering that median overall survival was 12-13 months in the two trials that established chemo-immunotherapy as treatment of ES SCLC, the study is designed to perform the primary survival analyses 14 months after last patient entry (to ensure that all survival data at 1 year are captured), which is a timepoint when we believe that the first signal of an effect of the experimental treatment can be seen. Additional survival analyses will be performed 2-, 3-, 4- and 5-year after last patient entry.

Median OS, PFS and time to progression in the brain will be estimated using the Kaplan-Meier method, and a Cox-model will be used for multivariable analyses adjusting for established prognostic factors in the target population (sex, PS, disease stage, presence of brain metastases and liver metastases) and age. Pearson's Chi-square test will be used to compare response rates (overall and in non-irradiated lesions), frequency of brain metastases, and location of metastases.

All HRQoL scores will be transformed to a scale of 0-100 according to the EORTC QLQ scoring manual. Mean scores will be compared at each assessment timepoint. A difference of 10 points is considered clinically relevant. Primary HRQoL-endpoints are dyspnea, global quality of life and physical function. All other HRQoL-scales will be included in complementary analyses.

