14.4 Determination of sample size

[figure not shown]
The sample size calculation assumes an accrual period of 30 months and that the primary survival analysis is performed 14 months after last patient entry. Additional survival analyses will be performed 2, 3, 4 and 5 years after last patient entry. All patients will be followed for a maximum of 5 years when the final survival

analysis will be performed.

Furthermore, the calculation is based on a constant hazard ratio of 0.65, corresponding to median survival times of 13.10 months for the control group and 20.02 months for the experimental group, and 1-year survival rates of 53% in the control group and 66% in the experimental group. This effect was selected as an effect of clinical relevance and an effect of this magnitude might be anticipated if there is a synergistic effect of combining radiotherapy with durvalumab.

The criterion for significance (alpha) has been set at 5%. The test is

2-tailed, which means that an effect in either direction will be interpreted. For this study design, alpha and tails, the population effect size described above, and to have power of 80% to yield a statistically significant result, 128 patients are required in each treatment group.

Enrolment will continue until 128 or more patients in the control arm have completed minimum three chemo-immunotherapy courses, and minimum 128 patients in the experimental group have completed minimum three chemo-immunotherapy courses plus TRT of 30 Gy. We expect a loss to follow-up and inability to complete three courses (plus TRT in the experimental group) of maximum 15% and estimate that we need to enroll a total of 302 patients.

All eligible patients who are randomized will be included in the primary efficacy analyses (ITT-population). All patients who commence chemo-immunotherapy will be included in the toxicity analyses. In addition, we will perform analyses of the patients who complete minimum three chemo-immunotherapy courses (and TRT in the experimental arm) (per protocol population). The sample size calculation was performed using SPSS Sample Power v3.

15. Ethical and regulatory requirements

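### The chi-square test on crude brain-metastasis frequency ignores time at risk, so a survival benefit alone can appear as excess brain metastases under TRT; separately, Kaplan-Meier overstates the risk if deaths are censored

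*Protocol*

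**What the plan says.** Protocol 14.1 lists "Frequency and timing of brain metastases" among the exploratory endpoints. Section 5.2 states the comparison ("Thus, we will compare the frequency and timing of brain metastases") and its purpose: if TRT and chemo-immunotherapy act synergistically, "the frequency of brain metastases may decrease in the experimental arm, or the time until brain metastases occur may be prolonged".

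Section 14.3.2 names the methods. On timing it says "Median OS, PFS and time to progression in the brain will be estimated using the Kaplan-Meier method", and the same sentence adds a Cox model for multivariable analyses, with baseline brain metastases among the covariates, without saying which outcomes that model covers. Pearson's chi-square is to compare response rates and also "frequency of brain metastases, and location of metastases". Nowhere does the protocol treat death as a competing event, give a censoring rule for time to brain progression, or adjust the frequency comparison for time at risk.

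The design expects unequal survival: 14.4 gives median survival of "13.10 months for the control group and 20.02 months for the experimental group".

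**The concern.** A patient can be counted with a brain metastasis only while alive and under observation. In the design's own scenario the TRT patients live longer, so they have longer in which the event can happen. An ever/never comparison by chi-square then tends to show more brain metastases under TRT even when TRT has no effect in the brain. That runs against the signal section 5.2 looks for, and does so in the very case where the trial succeeds on survival.

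The Kaplan-Meier problem is a different one. If a death without brain progression is treated as ordinary censoring, the curve describes a population in which nobody dies, and both the estimated risk and the median misstate what patients experience.

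**Working it through.** **Inputs from Protocol 14.4.** Medians 13.10 and 20.02 months, hazard ratio 0.65, accrual 30 months, primary analysis 14 months after last entry (so individual follow-up of 14 to 44 months), 302 patients (151 per arm).

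**Assumptions, not in the protocol.** Exponential times; a brain-progression hazard b, equal in both arms; death without brain progression at a fraction f of the overall-survival hazard; brain events ascertained until death or cut-off. I set b so that 1-KM at 12 months is 20, 30 or 40%: b = -ln(1-r)/12 = 0.0186, 0.0297, 0.0426 per month. I take f = 1 (near an upper case, because some deaths follow brain progression) and f = 0.5.

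**Step 1: reproduce the design.** Death hazards are ln2/13.10 = 0.0529 and ln2/20.02 = 0.0346, ratio 0.654. One-year survival is exp(-12 x 0.0529) = 53% and exp(-12 x 0.0346) = 66%, matching "53% in the control group and 66% in the experimental group". The probability of death by the analysis, 1 - [exp(-14h) - exp(-44h)]/(30h), is 0.761 and 0.617, mean 0.689. Freedman's 175 events give 175/0.689/2 = 127 per arm and the Lachin-Foulkes formula gives 129.7, against the stated 128. 256/0.85 rounds up to 302. The protocol gives no figure for the brain endpoint.

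**Step 2: crude frequency with no TRT effect in the brain.** For follow-up u and death hazard d, P = b/(b+d) x [1 - exp(-(b+d)u)], averaged over u from 14 to 44 months. The rejection rates are for a two-sided 5% chi-square at 151 per arm (4000 simulated trials for f = 1, normal approximation for f = 0.5).

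| 12-month 1-KM | f | Control | TRT | Excess (points) | Chi-square rejects |
|---|---|---|---|---|---|
| 20% | 1 | 22.1% | 26.7% | 4.6 | 17% |
| 30% | 1 | 31.8% | 37.9% | 6.1 | 19% |
| 40% | 1 | 40.7% | 47.9% | 7.1 | 25% |
| 20% | 0.5 | 29.2% | 32.6% | 3.4 | 9% |
| 30% | 0.5 | 41.3% | 45.7% | 4.4 | 12% |
| 40% | 0.5 | 51.8% | 56.8% | 5.0 | 14% |

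At a round b = 0.02 and f = 1 the frequencies are about 23% and 28%, with 16% rejection, nearly all of it (15.8%) in the direction of TRT harm. At b = 0.01 the test rejects in about 11 to 12% (f = 1) or 8% (f = 0.5). In the f = 1 rows, TRT has the higher count in 80 to 89% of trials.

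**Step 3: a true 20% cut in the brain hazard.** Replace b by 0.8b in the TRT arm. With f = 1 the crude frequencies become 22.1 vs 22.2%, 31.8 vs 32.2% and 40.7 vs 41.6%, so the benefit disappears. With f = 0.5 and the lowest b they are 29.2 vs 27.3%, so it is shrunk rather than erased.

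**Step 4: Kaplan-Meier with deaths censored (f = 1).** At 12 months 1-KM of 20, 30 and 40% stands against a cumulative incidence, from the same formula with u = 12, of 15.0, 22.6 and 30.4% (control) and 16.5, 24.9 and 33.3% (TRT): 1.2 to 1.3 times too high. At 24 months, 36, 51 and 64% stands against 21.3, 31.0 and 40.1% (control) and 25.2, 36.3 and 46.5% (TRT): 1.4 to 1.7 times too high. The Kaplan-Meier medians, ln2/b, are 37.3, 23.3 and 16.3 months. Yet the control cumulative incidence levels off at b/(b+d) = 26, 36 and 45%, so half of the control patients never have the event. The Kaplan-Meier curve is the same in both arms here, so it produces no arm difference.

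**Step 5: which comparison holds its level.** On the f = 1 simulated data the cause-specific log-rank test rejects in 4.7 to 5.1%. A Gray-type test on cumulative incidence rejects in 15 to 20%, because cumulative incidence also reflects the longer survival.

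**The case against.** The strongest case against runs as follows.

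- The endpoint is exploratory, has no alpha allocated and cannot touch the primary result. This stands, and it limits the weight of the point.
- The Cox model in the same sentence of 14.3.2, with deaths censored and baseline brain metastases as a covariate, would already be a cause-specific comparison of timing. This may be so, but the text does not say that the model covers brain progression, and it does not displace the chi-square named for frequency.
- The protocol plans a Kaplan-Meier median and does not define the event. If death counted as an event, the overstatement would not arise. This stands: censoring at death is the ordinary reading of an outcome named apart from PFS, but it is inferred.
- A higher absolute frequency among longer survivors is a real burden for patients. True; it misleads only when tested and read as an effect of TRT on the brain, which is the reading section 5.2 invites. Section 5.1.1 does foresee that better systemic control could leave the brain as a major site of failure.
- The sizes rest on an assumed brain hazard, and f = 1 is near an upper case. Both stand, which is why a range is given.

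A reader might go further and infer that the plan reverses the interpretation of the objective. The figures do not support that: even in the highest case about 75% of trials show no significant difference. A reader might also infer that the PCI question is misinformed, but section 4.4 frames that as a comparison of patients who receive PCI with those who do not, not of the randomized arms. Nor can one assume that brain-progression dates are complete: under section 2, patients who stop for progression are followed by local routine, with no brain MRI scheduled. Time under imaging therefore matters as well as survival, and the calculation does not model it.

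**Conclusion.** The point holds for the chi-square test. With the design's survival effect and no effect in the brain, it leans towards excess brain metastases under TRT and rejects in roughly 8 to 25% of trials instead of 5%; it can also mask a modest true reduction. The direction follows from unequal time at risk. The size rests on the assumed brain hazard, constant hazards, and the share of deaths that occur without brain progression.

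The Kaplan-Meier point is separate and conditional: if deaths are censored, the risk and the median are overstated, by about 1.4 to 1.7 times for the 24-month risk at f = 1. Each fault belongs to one method. Crude frequency does not overstate risk, and Kaplan-Meier does not create the arm difference. This is worth correcting before analysis, as a matter of interpretation of an exploratory endpoint.

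**What to change.** In 14.3.2:

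1. Make the between-arm comparison of brain progression a cause-specific Cox or log-rank test, stratified by or adjusted for baseline brain metastases, with death without brain progression named as the competing event. State explicitly that the Cox model already mentioned covers this outcome.
2. Estimate the risk of brain progression by Aalen-Johansen cumulative incidence instead of Kaplan-Meier.
3. Report crude frequency by arm as description only and drop the chi-square test for it.
4. Note in the interpretation that cumulative incidence alone would still show the survival-driven excess, so it cannot replace the cause-specific comparison. Note also that brain imaging is not scheduled after discontinuation for progression, and state how follow-up for this endpoint ends in those patients.

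The cost is a wording change and slight extra analysis work. No added patients or visits are needed, and the sample size and primary analysis are unchanged. Incomplete brain ascertainment after progression remains a limitation that the change of method does not remove.

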2. SCHEDULE OF STUDY ASSESSMENTS, PROCEDURES AND TREATMENT

Year	1										
Week	-4 to -1ab	0	3	3-4	3-4	6	9	11-12	13	13-15	17
	Screening	Durvalumab/ carboplatin/ etoposide 1	Durvalumab/ carboplatin/ etoposide 2	Response evaluation	Start of thoracic radiotherapy	Durvalumab/ carboplatin/ etoposide 3	Durvalumab/ carboplatin/ etoposide 4	Response evaluation	Durvalumab 5	Start of PCI	Durvalumab 6
Informed consent	Х										
Eligibility criteria	X										
Medical history, demography, height, tobacco use	X										
Clinical examination/ performance status/weight	Х	Х	Х			Х	Х	Х	Х		Х
ECG ^c	Х										
Concomitant medication	Х							Х	Х		Х
HRQoL (QLQ C30 + LC13)	Х							X			
Cognitive function (MoCA)	X							X			
Clinical chemistry ^{de}	X	Χ	X			X	X		X		X
Hematology ^f	Х	Xg	Xg			Xg	Xg				
Pregnancy test in women of childbearing potential ^h	X	Х	Х			X	X		X		Х
Hepatitis B&C, HIV if suspected	Х										
Pulmonary function ^j	Х							Х			
Assessment of adverse events	X	Χ	X			X	X	X	X	Х	X
CT thorax/upper abdomenk	X			ΧI				X			
MRI of the brain ^{k,m}	Х							X			
Collection of tumor tissue ⁿ	Х										
Blood biomarker analyses	Х			Х				Х			Х
Stool for biomarker analyses°	Х			Х				Х			Х
Randomization	X										L

^aEvery effort should be made to minimize the time between start of screening and starting treatment.

blf laboratory or imaging procedures were performed for alternate reasons prior to signing consent, these can be used for screening purposes with consent of the patient provided they were obtained within 28 days of randomization.

^cAny clinically significant abnormalities detected require triplicate ECG results.

If screening clinical chemistry and hematology assessments are performed within 5 days prior to Day 1 (first infusion day of each course), they do not need to be repeated at Day 1.

eBilirubin, aspartate aminotransferase (AST), alanine aminotransferase (ALT), alkaline phosphatase, creatinine, sodium (Na), potassium (K), thyroid stimulating hormone (TSH), free thyroxine (FT4), erythrocyte sedimentation rate (ESR), glucose, lactate dehydrogenase (LDH). Tri-iodothyronine (T3) or FT4 will only be measured if TSH is abnormal or if there is clinical suspicion of an AE related to the endocrine system.

^fHgB, leukocytes, neutrophil granulocytes, and platelets

^gOn day 1 and 10 of each chemotherapy course.

Study Number TRIPLEX
Protocol Version Number 1.1
Date 05-JAN-2022

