11.1.3 Screening phase

Screening procedures will be performed up to 28 days before Day 1 of the first chemo-immunotherapy course, unless otherwise specified. All patients must first read, understand, and sign the IRB/REB/IEC-approved ICF before any study-specific screening procedures are performed. After signing the ICF, completing all screening procedures, and being deemed eligible for entry, patients will be enrolled in the study. Procedures that are performed prior to the signing of the ICF and are considered standard of care may be used as screening assessments if they fall within the 28-day screening window.

The following procedures will be performed during the screening visit:

- Informed Consent
- Review of eligibility criteria
- Medical history, demographics, and smoking history
- Complete physical exam
- ECOG Performance Status
- Weight and height
- 12-lead ECG (in triplicate if there are any significant abnormalities on the first ECG, each recording should be made 2-5 minutes apart)
- Review of prior/concomitant medications
- CT of the thorax and upper abdomen
- MRI of the brain
- Pulmonary function
- Cognitive function (MoCA test)
- HRQoL-questionnaire
- Pregnancy test in women of childbearing potential
- Collection of blood and stool samples for biomarker analyses including neuronal auto-antibodies
- Clinical laboratory tests for:
 - Hematology (see Table 4)
 - Clinical chemistry (see Table 5)
 - Creatinine Clearance
 - Serum pregnancy test (for women of childbearing potential only)

Hepatitis serologies

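### Section 14.3.2 plans HRQoL as a visit-by-visit comparison of means on three primary scales, with no stated use of the baseline score or the repeated measurements

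*Protocol*

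**What the plan says.** The HRQoL analysis is set out in Protocol section 14.3.2. Scores are put on the 0-100 EORTC scale, and then "Mean scores will be compared at each assessment timepoint". The yardstick is "A difference of 10 points is considered clinically relevant". The scales are ranked: "Primary HRQoL-endpoints are dyspnea, global quality of life and physical function", and "All other HRQoL-scales will be included in complementary analyses".

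The data behind this are longitudinal. Section 11.1.3 lists the "HRQoL-questionnaire" among the screening procedures. In the section 2 schedule, the row that begins "HRQoL (QLQ C30 + LC13" is marked at screening and then at nine scheduled visits: week 11-12; year 1 weeks 21, 29, 37 and 45; year 2 weeks 1, 17, 33 and 49. One further questionnaire is due at progression or loss to follow-up.

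Section 14.1 lists "Health-related quality of life" as a secondary endpoint. Section 5.1.1 gives the reason: added toxicity from TRT cannot be ruled out, so adverse events and patient-reported HRQoL will be compared between arms. Section 14.3.2 names no test, alpha, covariate, longitudinal model or key visit for HRQoL.

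**The concern.** The sentence describes a series of separate cross-sectional comparisons. Read that way, the plan leaves two things unused. The screening score is collected from every patient and would normally reduce the variance of the arm difference. Earlier scores from patients who later stop responding would not inform later visits.

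The second matters here because attrition is heavy. Many patients will have died before the later visits, and the notes under the section 2 schedule move patients who stop study treatment for progression to follow-up by local routines.

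There are also 27 comparisons on scales labelled primary, and nothing says which visit answers the question. HRQoL is one of the ways the trial looks for harm from TRT. An imprecise analysis could miss a real difference, and one isolated nominal finding among 27 would be hard to interpret.

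**Working it through.** The protocol gives no power, sample size or error rate for HRQoL, so there is no figure of its own to reproduce.

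**Number of comparisons.** Post-baseline visits by schedule table: 1 + 7 + 1 = 9. Three primary scales × 9 visits = 27.

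**Precision.** Adjusting for a baseline score whose correlation with the outcome is rho multiplies the variance of the arm difference by 1 − rho². The protocol does not give rho, so the values are assumptions.

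| rho | 1 − rho² | Equivalent gain in patients, 1/(1 − rho²) − 1 |
|---|---|---|
| 0.3 | 0.91 | 10% |
| 0.4 | 0.84 | 19% |
| 0.5 | 0.75 | 33% |
| 0.6 | 0.64 | 56% |
| 0.7 | 0.51 | 96% |

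**Attrition through death alone.** Inputs from section 14.4: medians of 13.10 and 20.02 months and 302 patients, so 151 per arm. Year 2 week 49 is week 52 + 49 = 101, or 101/4.345 = 23.2 months. With exponential survival:

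- Control: 151 × exp(−ln 2 × 23.2/13.10), about 44 alive.
- Experimental: 151 × exp(−ln 2 × 23.2/20.02), about 68 alive.

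Under the design assumptions, late means therefore compare differently selected survivors.

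**Chance of at least one nominal p<0.05 under no effect.** This needs a test level. Section 14.4 states 5% two-tailed only for the survival sample size, so using it for HRQoL is an assumption. If the 27 tests were independent: 1 − 0.95^27 = 0.75. For correlated tests, 200,000 draws of 27 normal variables, with equal correlation between visits, gave:

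| Between-visit correlation | Scale correlation 0.3 | 0.5 | 0.7 |
|---|---|---|---|
| 0.5 | 0.59 | 0.56 | 0.50 |
| 0.6 | 0.54 | 0.50 | 0.45 |
| 0.7 | 0.47 | 0.44 | 0.39 |
| 0.8 | 0.40 | 0.37 | 0.33 |
| 0.9 | 0.31 | 0.29 | 0.25 |

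This is roughly 25% to 60%. Autoregressive correlation (0.3 to 0.9) gave 34% to 73%. Equal correlation (0.3 to 0.8) with deaths at the protocol's survival assumptions gave 40% to 69%.

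**Requiring 10 points as well.** The same simulation with deaths was repeated for three pairs of between-visit and scale correlation: 0.5/0.3, 0.6/0.5 and 0.8/0.5. Nominal significance alone gave 45% to 63%. Requiring p<0.05 and a difference of at least 10 points gave:

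| SD (assumed) | All survivors respond | 70% complete |
|---|---|---|
| 20 | about 4% | 12-16% |
| 25 | 15-21% | 29-41% |
| 30 | 30-42% | 41-57% |

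**The case against.** The strongest reply is that the sentence is silent, not wrong. It names no model and could be met by visit contrasts from a baseline-adjusted mixed model. Details of a secondary patient-reported endpoint are commonly left to the SAP, which was not available for this review. This stands in part: the protocol does not exclude baseline adjustment. But section 14.3 does state methods, including covariates for the Cox model, and the analyses it expressly defers to a later plan are the biomarker ones. The point is about the HRQoL method it states.

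A reader might infer that the comparison is biased because baseline is left out. The documents do not support that. Under randomization an unadjusted comparison is valid, and omitting baseline in itself costs precision only. Selective dropout and death are a separate matter.

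A reader might also infer that the plan carries a 35% to 75% chance of a spurious difference. That is not a property of the text. No HRQoL alpha is stated, 75% requires independence between repeated measurements on the same patients, and the figure falls to about 25% at very high correlation. It is often lower still if the 10-point yardstick must also be met, although the protocol does not make that a joint criterion with significance.

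The protocol already limits multiplicity in part by making all other scales complementary. Finally, one key visit with Holm adjustment would reduce sensitivity to harm, including late harm. That objection stands, so neither is presented here as necessary.

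**Conclusion.** The point holds as a loss of efficiency in a stated method for a secondary endpoint. The protocol fixes a visit-by-visit comparison on three primary scales at nine visits, and states no use of the baseline or repeated scores it collects.

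The gain from baseline adjustment is a 16% to 36% reduction in variance at an assumed correlation of 0.4 to 0.6. The direction is secure for any appreciable correlation; the size is not given by the documents. A longitudinal model would also use earlier scores from patients who later stop responding. It would not resolve truncation by death, and estimates at late visits need cautious reading under either method.

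The multiplicity figure of roughly 25% to 60% is conditional on 5% two-sided tests at all 27 points and on the assumed equal correlations. It illustrates the lack of a key timepoint and is not an error rate of the plan. Nothing here affects the primary survival analysis.

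**What to change.** Replace the sentence in section 14.3.2 with: *Each primary HRQoL scale is analysed in a longitudinal mixed model over all scheduled visits, with visit-by-arm terms and with the baseline score and the stratification factors (liver and brain metastases) as covariates; arm differences with 95% confidence intervals are reported at each visit.*

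Naming one key timepoint per scale and a multiplicity rule is optional and for the sponsor to decide, given that HRQoL is also meant to detect harm. For orientation, one visit per scale would leave three tests: 1 − 0.95³ = 14.3% if independent at 5% each, or at most 5% with Holm.

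The cost is a change of wording. It needs no new data, visits or patients. If the SAP already specifies such a model, the protocol sentence only needs to be brought into line with it.
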